1.2. Study Objectives

The overall objective of this study is to evaluate the safety and tolerability of the NT-501 implant, when implanted in both eyes of participants with MacTel type 2.

This statistical analysis plan (SAP) is designed to outline the methods to be used in the analysis of study data in order to answer the study objective(s). Populations for analysis, data handling rules, statistical methods, and formats for data presentation are provided. The statistical analyses and summary tabulations described in this SAP will provide the basis for the results sections of the clinical study report (CSR) for this trial.

This SAP will also outline any differences in the currently planned analytical objectives relative to those planned in the study protocol.

1.3. Study Design

1.3.1. Synopsis of Study Design

This is a multicenter, open-label study to evaluate the safety of bilateral NT-501 implants in a minimum of 30 study participants with MacTel type 2. All study subjects who have received a NT-501 implant in one eye, completed either the Phase 1/2 extension study (NTMT-01/02E) or the Month-24 visit of the Phase 3 study (NTMT-03) and meet the eligibility criteria, will receive a NT-501 implant in their fellow eye and will be followed for 6 months following NT-501 implantation.

Study participants will have a screening period of up to 28 days. Participants who meet the inclusion/exclusion criteria will have implant surgery within 30 days of the Screening Visit. After the surgery, subjects receiving a NT-501 implant will return to the clinical center for assessments performed on Day 1, Week 1 (\pm 2 days), Month 1 (\pm 7 days), Month 3 (\pm 14 days) and Month 6 (\pm 14 days). Upon completion of the 6-month visit, these participants will exit the study. These participants may elect to be followed for safety and disease progression in a nested substudy of the existing Natural History and Observation and Registry Study of Macular Telangiectasia Type 2 (NHOR).

1.3.2. Randomization Methodology

No randomization will be performed for this study. All subjects will receive an additional NT-501 implant in their study eye.

1.3.3. Stopping Rules and Unmasking

There are no formal stopping rules. This is a single-arm, open label study thus unmasking of subjects or study personnel to study treatment is not a concern.

1.3.4. Study Procedures

The schedule of assessments, as outlined in the study protocol, is provided in Table 1-1.

Table 1-1 Schedule of Assessments

| Procedures | Screening Day -28 to -1 | Surgery Day 0 | Post-Surgery Day 1 | Post-Surgery Week 1 | Post-Surgery Month 1 | Post-Surgery Month 3 | Post-Surgery Month 6 |
|--|-------------------------|-----------------|--------------------|---------------------|----------------------|------------------------|----------------------|
| Visit Window | | | | ±2 days | ±7 days | ± 14 days | ±14 days |
| Visit Number | 1 | 2 | 3 | 4 | 5 | 6 | 7 |
| STUDY DAY | -28 to -1 | 0 | 1 | 7 | 30 | 90 | 180 |
| Informed Consent | X | | | | | | |
| Demographics | X | | | | | | |
| Medical & Ophthalmic History ^a | X | X | | | | | |
| Concomitant Medications and non-study procedures | X | X | X | X | X | X | X |
| Adverse Events | | X | X | X | X | X | X |
| Vital Signs ^b | X | | | | | | |
| Inclusion/exclusion criteria | X | | | | | | |
| Eligibility Review | X | X | | | | | |
| Medical evaluation ^c | X | X | | | | | |
| Pregnancy Test ^d | X | | | | | | |
| Serum Chemistry, Hematology & Urinalysis | X | | | | | | |
| Visual Acuity (BCVA) | OU ^e | SE ^f | | SE ^f | OU ^e | O U ^e | OU ^e |
| Measurement of pupil diameter | OU | | | | OU | O U | OU |
| Complete Ophthalmic Exam ^g | OU | | SE | SE | OU | O U | OU |
| Dilated Fundus Photography | OU | | | | | | OU |
| SD-OCT ^h | OU | | | SE | OU | O U | OU |
| Fluorescein Angiography | OU | | | | | | |
| Serum concentrations of CNTF, Ab or Nab to CNTF, Ab to NTC-201.6A cells; or Ab to DFHR (serum) | X | | | | X | X | X |

| Procedures | Screening Day -28 to -1 | Surgery Day 0 | Post- Surgery Day 1 | Post- Surgery Week 1 | Post- Surgery Month 1 | Post- Surgery Month 3 | Post- Surgery Month 6 |
|---|-------------------------------|------------------|---------------------------|----------------------------|-----------------------------|-----------------------------|-----------------------------|
| Visit Window | | | | ±2 days | ±7 days | ± 14 days | ±14 days |
| Visit Number | 1 | 2 | 3 | 4 | 5 | 6 | 7 |
| NT-501 implantation surgery | | X | | | | | |
| Post NT-501 implant assessment | | | SE | SE | OU | O U | OU |
| External photograph of conjunctiva over implant | | | | | OU | O U | OU |
| Complete Exit Form | | | | | | | X |

Abbreviations: BCVA= Best Corrected Visual Acuity; SD-OCT = spectral domain optical coherence tomography, OU = both eyes, SE = study eye

- a Demographic data includes height, weight, eye color and smoking history
- b Vital signs include body temperature, pulse rate, respiration rate and sitting blood pressure
- c The medical evaluation may be performed during screening or on the day of surgery; the evaluation is standard for any surgical procedure or anesthesia (the tests performed will be site-specific)
- d Females of childbearing potential only; additional pregnancy tests may be performed at any time/day during study
- e Manifest refraction will be performed prior to BCVA assessments except for the BCVA assessments performed prior to surgery and 1 week following surgery
- f Best-corrected visual acuity must be performed within 1 week prior to the day of surgery
- g Complete ophthalmic exam consists of an external examination of the eye and adnexa, screening for eyelid/pupil responsiveness, slit lamp biomicroscopy, dilated fundus examination, indirect ophthalmoscopy, and IOP assessment) Slit lamp biomicroscopy, indirect ophthalmoscopy and intraocular pressure (IOP). IOP measurements will be taken prior to pupil dilation. If possible, IOP measurements should take place at approximately the same time of the day at each visit and with the same equipment
- h The same SD-OCT instrument should be used for an individual participant throughout the entire study

1.3.5. Safety Parameters

Safety will be evaluated by monitoring AEs and SAEs, complete ophthalmic exam (consisting of an external examination of the eye and adnexa, screening for pupil responsiveness, slit lamp biomicroscopy, dilated fundus examination, indirect ophthalmoscopy, and IOP), and measurement of BCVA.

All AEs will be captured whether or not considered to be related to the surgical procedure, implant, or CNTF. An attempt will be made to differentiate between treatment-related AEs and AEs considered to be part of normal progression of the disease. In addition, for treatment-related AEs, an attempt will be made to differentiate those that the investigator believes are due to the implant itself, to CNTF, or to the implant procedure.

Safety will be assessed as noted in the Schedule of Events (SOE). The following assessments will be performed at the time points indicated in the SOE.

- Adverse Events
- Vital Signs
- Pregnancy Test
- Complete ophthalmic exam (consisting of an external examination of the eye and adnexa, screening for pupil responsiveness, slit lamp biomicroscopy, dilated fundus examination, indirect ophthalmoscopy, BCVA and IOP)
- SD-OCT
- Serum chemistry, hematology, and urinalysis
- Antibodies (Ab) or Neutralizing antibodies (Nab) to CNTF, Ab to NTC-201.6A cells and Ab to DFHR (serum)
- Serum levels of CNTF

1.3.6. Primary Safety Parameters

Safety evaluations that will be performed during the study include physical examinations, measurement of vital signs, clinical laboratory evaluations including hematology, serum chemistry, and urinalysis, and monitoring of adverse events and concomitant medications. Serum chemistry, hematology, and urinalysis will be performed only at baseline.

Primary safety endpoints are:

- Number and proportion of adverse events from day of surgery through 6 months post implantation
- Number and proportion of severe adverse events from day of surgery through 6 months post implantation
- Number and proportion of ocular adverse events from day of surgery through 6 months post implantation
- Number and proportion of non-ocular adverse events from day of surgery through 6 months post implantation

1.3.7. Secondary Safety Parameters

Secondary safety endpoints are:

- Number and proportion of participants with a loss in BCVA of 15 or more letters from baseline in the study eye using the Early Treatment Diabetic Retinopathy Study (ETDRS) distance chart
- Number and proportion of participants with at least 1 treatment-emergent serious adverse event (SAE)
- Detectable serum levels of CNTF at Months 1, 3 and 6 post-implantations of NT-501
- Number and proportion of participants with serum Ab or Nab to CNTF, Ab to NTC-201.6A cells and Ab to DFHR at Baseline and Months 1, 3 and 6 post-implantation of NT-501

2. SUBJECT POPULATION

2.1. Population Definitions

All analyses will be performed using the Safety Population.

- Safety Population: All subjects who receive a NT-501 implant in the study eye and have at least 1 safety measurement. No participant (or data) will be excluded from the safety population because of protocol violations that occur during the study.

2.2. Protocol Violations

The Sponsor or designee will be responsible for producing the final protocol violation file (formatted as a Microsoft Excel file), in collaboration with Veristat and the data monitoring group as applicable; this file will include a description of the protocol violation. This file will be finalized prior to hard database lock.

All protocol violations will be presented in a data listing.

3. GENERAL STATISTICAL METHODS

3.1. Sample Size Justification

Formal sample size calculations were not performed. The number of participants was chosen based on feasibility and is considered sufficient to meet the study objectives.

3.2. General Methods

All data listings that contain an evaluation date will contain a relative study day (Rel Day). Pre-treatment and on-treatment study days are numbered relative to the day of surgical implantation of the NT-501 device in the fellow eye which is designated as Day 0. The preceding day is Day -1, the day before that is Day -2, etc. Post-surgical study days are numbered relative to the last dose and are designated as Day 1, Day 2, etc.

All output will be incorporated into Microsoft Word or Excel files, or Adobe Acrobat PDF files, sorted and labeled according to the International Conference on Harmonisation (ICH) recommendations, and formatted to the appropriate page size(s).

Tabulations will be produced for appropriate demographic, baseline, and safety parameters. For categorical variables, summary tabulations of the number and percentage of subjects within each category (with a category for missing data) of the parameter will be presented. For continuous variables, the number of subjects, mean, median, standard deviation (SD), minimum, and maximum values will be presented.

This study is primarily descriptive in nature; therefore, there are no formal statistical hypothesis tests planned. Data will be presented by subject and summarized overall.

3.3. Computing Environment

All descriptive statistical analyses will be performed using SAS statistical software Version 9.4 or later

3.4. Baseline Definitions

For all analyses, baseline will be defined as the most recent measurement prior to surgical implantation of the NT-501 device in the study eye. Prior to enrollment into the NTMT-02B study, all subjects previously received an implant as part of their participation in either the Phase 1/2 extension study (NTMT-01/02E) or the Phase 3 study (NTMT-03). As a result, participants' fellow eyes in the prior studies will be the study eye in the current study.

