6.3 Study Visit Procedures

6.3.1 Visit 1: Screening/Baseline Procedures

Subjects who have completed the NTMT-01/02 extension study and have an NT-501 implant are eligible for screening. Subjects who have completed the Month-24 visit of the Phase 3 study and wish to be considered for entry into the Bilateral Implant Safety Study, must exit the Phase 3 study prior to participating in the Screening Visit for the Bilateral Implant Safety Study. Participants who sign the consent form and begin screening will be assigned a participant identification number by the Advantage eClinical system. Screening procedures may be completed over more than 1 day to accommodate schedules and to lessen participant burden. All screening evaluations should be completed within 28 days of signing the Informed Consent to establish eligibility.

Once the individual has indicated interest in participation, the principal investigator or appropriate designee must obtain the participant's written consent. Once the consent is obtained, the investigator may initiate screening assessments. The results of all screening evaluations must be reviewed, and the participant must be found eligible prior to surgery. Once a participant is determined to be eligible for the study, surgery should be completed within approximately 30 days of the Screening visit.

The screening examinations and imaging must include the following:

- Informed consent
- Demographics; medical and ophthalmic history, including height, weight, eye color and smoking history
- Concomitant medications and non-study procedures
- Inclusion/exclusion criteria
- Vital signs (body temperature, pulse rate, respiration rate and sitting blood pressure)
- Medical evaluation, standard for any surgical procedure and its associated anesthesia (the specific tests to be ordered will be site-specific), may be performed during screening period or on the day of surgery
- Blood and urine sample collection for serum chemistry, hematology, urinalysis
- Urine or blood pregnancy exam for female participants of childbearing potential

- Blood sample collection for analysis of Ab and Nab to CNTF, Ab to NTC-201.6A cells and Ab to DFHR
- Blood sample collection for analysis of serum levels of CNTF
- BCVA following manifest refraction (both eyes)
- Complete ophthalmic exam (consisting of an external examination of the eye and adnexa, screening for pupil responsiveness, slit lamp biomicroscopy, indirect ophthalmoscopy, and IOP) (both eyes)

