6.3.2 Visit 2: Enrollment and Surgery

If the participant meets all study criteria and agrees to participate in the study, then the implant surgery date should be identified. The implant surgery procedure should be completed within one month of the Screening visit.

On the date of the surgery, the investigator will confirm that no change in the participant's general condition has occurred that would exclude study participation.

The following evaluations/procedures will be conducted during this visit:

- Eligibility review
- Medical evaluation that is standard for any surgical procedure and its associated anesthesia (the specific tests to be ordered will be site-specific), unless the medical evaluation was performed during screening period
- Record any further medical/ophthalmic history
- Record any additional concomitant medications and non-study procedures
- Perform AE assessment (from the time surgery begins)
- Assess BCVA (may be performed within 1 week prior to the day of surgery or on the day of surgery, manifest refraction is not required)
- NT-501 implant surgery

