6.3.4 Visit 4: 1 Week Post-surgery (+/- 2 days)

Participants must return to the clinic 1-week post-surgery and will undergo the following procedures:

- AE assessment
- Review concomitant medications and non-study procedures
- BCVA in study eye only (manifest refraction is not required)
- Complete ophthalmic exam of study eye (consisting of an external examination of the eye and adnexa, screening for pupil responsiveness, slit lamp biomicroscopy, indirect ophthalmoscopy, and IOP) in study eye only
- SD-OCT in study eye only
- Implant site examination in study eye only

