4.4.2. BCVA

The number and percent of subjects with a loss in BCVA of 15 or more letters from baseline in the study eye at any follow-up study visit and by each study visit and the associated 95%

confidence intervals will be tabulated. Confidence intervals will be based on the Clopper-Pearson method.

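### The study-eye BCVA baseline is normally the Visit 2 value, for which refraction is not required, but it is compared with refracted values at Months 1, 3 and 6; if it reads low, true 15-letter losses can go uncounted

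*SAP*

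**What the plan says.** SAP 3.4 sets a single baseline rule: "For all analyses, baseline will be defined as the most recent measurement prior to surgical implantation of the NT-501 device in the study eye". Neither that section nor SAP 4.4.2 makes an exception for BCVA.

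Two pre-surgery BCVA measurements of the study eye are planned:

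- **Screening (Visit 1).** Protocol 6.3.1 requires BCVA in both eyes after manifest refraction.
- **Visit 2.** Footnote f to SAP Table 1-1 says "Best-corrected visual acuity must be performed within 1 week prior to the day of surgery". Protocol 6.3.2 also allows the day of surgery itself and adds that "manifest refraction is not required". Footnote e agrees: "Manifest refraction will be performed prior to BCVA assessments except for the BCVA assessments performed prior to surgery and 1 week following surgery".

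After surgery, Week 1 BCVA is taken in the study eye without required refraction (Protocol 6.3.4). BCVA at Months 1, 3 and 6 follows manifest refraction (Protocol 6.3.5 to 6.3.7).

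The endpoint that uses the baseline is in SAP 4.4.2, which tabulates how many participants, and what share of them, meet this criterion: "loss in BCVA of 15 or more letters from baseline in the study eye at any follow-up study visit and by each study visit". Clopper-Pearson 95% intervals are planned for it.

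**The concern.** The most recent value is a sound default when all measurements are made in the same way. Here they are not. The Visit 2 value is normally later than Screening and so becomes the baseline. At Months 1, 3 and 6 a refracted score is then set against one for which refraction was optional, although a refracted pre-surgery score is already in the data.

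Leaving out a fresh refraction would be expected to lower an acuity score, if it changes it at all. A low baseline shrinks the observed loss. At the refracted visits the error therefore runs towards apparent safety, in a study whose purpose is safety.

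Loss of 15 or more letters is the only BCVA endpoint (Protocol section 3; SAP 1.3.7). With a minimum of 30 participants it will rest on very few events, and with no hypothesis test planned, the count and its interval are the result.

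**Working it through.** **Inputs from the documents.** Threshold of 15 letters (SAP 4.4.2); n = 30, the planned minimum (Protocol 5.1; SAP 1.3.1); refraction status by visit as set out above. There is no sample-size or power figure to reproduce, because no formal calculation was made (SAP 3.1).

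**Inputs assumed.** The documents give no value for d (letters by which the Visit 2 score reads low), nor for the mean or SD of BCVA change. The illustration takes true loss as normal with mean 2 letters and SD 7 or 10, and gives every participant the same d, from 0 to 3.

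**Step 1: direction.** Observed loss = true loss − d. Counting requires true loss − d ≥ 15, that is, true loss ≥ 15 + d. For d = 1, 2, 3 the effective threshold is 16, 17, 18 letters.

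**Step 2: proportion counted at one refracted visit.** P(counted) = 1 − Φ((15 + d − 2)/SD). For example, SD 7 and d = 2 gives 1 − Φ(15/7) = 1 − Φ(2.143) = 1.61%, and 30 × 0.0161 = 0.48 participants.

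| d | SD 7: % counted | expected of 30 | SD 10: % counted | expected of 30 |
|---|---|---|---|---|
| 0 | 3.16 | 0.95 | 9.68 | 2.90 |
| 1 | 2.28 | 0.68 | 8.08 | 2.42 |
| 2 | 1.61 | 0.48 | 6.68 | 2.00 |
| 3 | 1.11 | 0.33 | 5.48 | 1.64 |

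**Step 3: chance that at least one true loss is missed.** Let p = P(15 ≤ true loss < 15 + d), the difference between the d = 0 row and the row for d. The chance is 1 − (1 − p)^30.

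- SD 7: d = 1, p = 0.89%, chance 23.5%; d = 2, p = 1.56%, chance 37.6%.
- SD 10: d = 1, p = 1.60%, chance 38.4%; d = 2, p = 3.00%, chance 59.9%.

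**Step 4: what one missed case does.** The Clopper-Pearson 95% interval is 0 to 11.6% for 0/30 and 0.1% to 17.2% for 1/30.

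**Step 5: Week 1 and the any-visit count.** Week 1 is also exempt from refraction. Against a Visit 2 baseline the method roughly matches, but a Week 1 score can fall for refractive reasons alone and add to the any-visit count. The later visits can lose cases while Week 1 adds them, so the net direction of the any-visit count is not fixed. The downward bias applies to the Month 1, 3 and 6 rows, and to the part those visits contribute to the any-visit count.

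**The case against.** The strongest objection is that everything depends on d, and d may be nil. Not requiring a new refraction does not mean testing uncorrected vision. The test is still best-corrected acuity under the ETDRS procedure by a certified technician (Protocol 6.2.1), and a Screening refraction about a month old at most is available for reuse. Procedure-specific instructions, mentioned in the protocol but not among the documents reviewed, may settle which correction is worn. This stands as a limit on size. It does not answer the point, because the protocol and SAP do not say which correction is worn, and optional refraction lets the baseline method vary between sites.

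The figures above are one-sided and apply one d to everyone. A repeat test could also read higher than Screening: under the same model, d = −1 would give 4.3% (SD 7) or 11.5% (SD 10) instead of 3.2% or 9.7%. If only 20% of participants were affected, the chances in Step 3 fall to 5% and 9% (SD 7; d = 1, 2) and to 9% and 17% (SD 10). Both points are fair. The figures illustrate the mechanism and do not estimate what will happen in this trial.

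A missed loss could still be found in the listings, or be reported as an adverse event if it is clinically significant and needs intervention (Protocol section 9). Neither route corrects the tabulated count or its interval.

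The last value before intervention is conventional and closest to surgery. That is a real advantage, but the gap is small: participants "will have implant surgery within 30 days of the Screening Visit". Nor is it certain that Visit 2 always supplies the baseline. A refracted Screening BCVA within a week of surgery might satisfy footnote f, which is why the point is stated as what normally happens.

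**Conclusion.** The concern holds. As written, the rule normally takes as baseline a study-eye BCVA for which refraction is not required, and compares it with refracted values at Months 1, 3 and 6. Each letter by which that baseline reads low raises the effective threshold by one letter at those visits.

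The size is unknown. Under the assumptions shown, a true rate of 3.2% at one visit would be reported as 2.3%, 1.6% or 1.1% for d = 1, 2 or 3 (SD 7), and a true 9.7% as 8.1%, 6.7% or 5.5% (SD 10). If d = 0 nothing changes. No net direction is claimed for the any-visit count.

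The endpoint is secondary and descriptive, so this does not threaten the study's main conclusions. The change is still worth making, because a possible bias towards apparent safety can be removed with data already being collected.

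**What to change.** In SAP 3.4 and 4.4.2:

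1. Define the BCVA baseline for Months 1, 3 and 6 as the last pre-surgery BCVA obtained with manifest refraction, normally Screening.
2. Use the Visit 2 value as the reference for Week 1.
3. Keep the by-visit table and the any-visit count including Week 1, so that early postoperative loss is not dropped. State that this count uses the visit-specific reference.
4. Add one count of 15-letter loss over the refracted visits only (any of Months 1, 3 and 6).
5. Add one sensitivity table using the Visit 2 baseline throughout, to show whether the choice of baseline changes the result.

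The cost is SAP wording, one count and one table, ideally settled before database lock. No visit or procedure is added. The downside is that the refracted baseline may be up to about 30 days old at surgery.
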